3.1.2.2 Prevalence of Treatment Failures

The following cases will be considered treatment failures:

- Persistent bleeding at the TBS beyond T₄
- Grade 3 or Grade 4 breakthrough bleeding from the TBS that jeopardizes subject safety according to the investigator's judgment at any moment during the 10-minute observational period and until T_{Closure}
- Use of alternative hemostatic treatments or maneuvers (other than the study treatment) at the TBS during the 10-minute observational period and until $T_{Closure}$, or use of study treatment at the TBS beyond T_4 and until $T_{Closure}$
- Rebleeding (Grade ≥1) at the TBS after the assessment of the primary efficacy endpoint at T₄ and until T_{Closure}

In the event of Grade 3 or Grade 4 breakthrough bleeding that jeopardizes subject safety according to the investigator's judgment at the TBS at any moment during the 10-minute observational period and until the completion of the surgical closure by layers of the exposed

^a Any missing to the question will be deemed "No".

^b Any missing to the question will be deemed "Yes".

Grifols Worldwide Operations, Ltd

Page 10 of 18

surgical field, the surgeon may use any other hemostatic measures at his/her discretion if
deemed necessary (use of FS Grifols, EVICEL, or other plasma-derived hemostatic agents
are not allowed in this case). In such a case, the subject will be considered a treatment failure.

The alternative treatment used will be recorded in the subject's source documents and
electronic case report forms (eCRFs).

3.1.3 Exploratory Efficacy Variables

- The proportion of subjects achieving at least 1 point decrease in bleeding intensity according to the 5-point validated bleeding severity scale by the defined observation time points of T₄, T₇, and T₁₀
- The mean change from baseline in bleeding intensity according to the 5-point validated bleeding severity scale at the defined observation time points of T₄, T₇, and T₁₀

3.2 Safety Variables

- Adverse events (AEs) including serious adverse events (SAEs), suspected adverse drug reactions (ADRs)/adverse reactions (ARs), and discontinuations due to AEs
- Clinical laboratory panels (i.e., coagulation panel, hematology, serum clinical chemistry)
- Physical examination
- Vital signs

4 GENERAL STATISTICAL CONSIDERATIONS

Statistical analyses and data presentations will be generated using SAS version 9.4 or higher.

Unless otherwise noted, for continuous variables, descriptive statistics will include the number of non-missing values, mean, standard deviation, median, minimum and maximum. For categorical variables, descriptive statistics will include counts and percentages per category. All statistical inference will be tested at 2-sided with α =0.05.

Unless otherwise noted, all data collected in the eCRFs or electronically transferred (such as central laboratory data) will be presented in data listings. Subjects will be identified in the data listings by subject number (which includes site number) and grouped by different treatment groups.

For table summaries, the data will be presented at the scheduled visits according to protocol. Any data collected at the unscheduled visits will be listed.

4.1 Data Handling

Unless otherwise noted, if an observation is missing at a specific scheduled visit/timepoint, the value at that visit will not be imputed and will be set to missing except for the hemostasis assessment that a missing hemostasis assessment at a time point would be deemed not to have achieved hemostasis at that specific time point only.

Grifols Worldwide Operations, Ltd Page 11 of 18

Unless otherwise noted, baseline will be defined as the last non-missing measurement prior to the start of the study treatment application

This is a single-blind study. Treatment assignment for subjects participating in the study will be blinded from the sponsor, except for personnel from study drug supply groups. Treatment allocation will only be unblinded as necessary within Grifols Global Pharmacovigilance group for subjects that experience a serious and unexpected ADR, as defined in protocol Section 8.3.7, and reported according to the procedure described in protocol Section 8.3.9.1.

4.2 Analysis Populations

Intent-to-treat (ITT) population

ITT population includes all subjects who are randomized, regardless of meeting intraoperative enrollment criteria and regardless of whether the investigational product (IP) was administered to the subject.

Modified ITT (mITT) population

mITT population includes all subjects in the ITT population who meet intra-operative enrollment criteria, and thus treated with any amount of IP.

Per Protocol (PP) population

PP population includes all subjects in the mITT population who do not have any major protocol deviations (to be determined at a data review meeting prior to unblinding) which could impact the analysis of primary efficacy endpoint.

Safety population

Safety population includes all subjects who receive any amount of IP.

4.3 Sample Size Considerations

The sample size of the study was estimated to provide sufficient power (at least 80%) to demonstrate the hemostatic efficacy of FS Grifols in parenchymous and soft tissue surgery.

Assuming that the true response rate is 80% for the FS Grifols group and 80% for the EVICEL group, it can be shown that a sample size of 172 subjects (86 subjects in the FS Grifols treatment group and 86 subjects in the EVICEL treatment group, with a 1:1 assignment ratio) would give a power of at least 80% to establish non-inferiority, with lower 95% CI for the ratio of the proportion of subjects with hemostasis success by 4 minutes in the 2 treatment groups (FS Grifols relative to EVICEL) above 0.80.

The approximate number of subjects planned to be randomized according to age range will be as follows:

Grifols Worldwide Operations, Ltd Page 12 of 18

- Adolescents (12 to 17 years): approximately 100
- Children (2 to 11 years): approximately 50
- Infants and toddlers (28 days to 23 months): approximately 16
- Preterm (up to gestational age <37 weeks) and term newborn infants (0 to 27 days): approximately 6

4.4 Interim Analysis

No interim analysis is planned to be performed.

5 SUBJECT DISPOSITION

Subject disposition will include the number of subjects screened, number of subjects randomized, number and percentage of subjects in each analysis population, and number and percentage of subjects completing the study by treatment groups.

The number and percentage of subjects discontinuing early from the study after the study treatment will be summarized for primary reasons of discontinuation. Also, the number and percentage of pre-operative screen failures and intra-operative screen failures will be summarized for primary reasons of ineligibility.

Disposition status will be listed for all subjects.

6 PROTOCOL DEVIATIONS

Protocol deviations will be identified and evaluated during the study and finalized before the database lock. The type of protocol deviations and severity (e.g., minor, major, and critical) will be summarized by treatment groups. The type and severity of protocol deviations, subject specific or general site protocol deviations will also be listed.

7 DEMOGRAPHY AND MEDICAL HISTORY

7.1 Demographic and Baseline Characteristics

Demographic and baseline characteristics including sex, race, ethnicity, age at randomization (years) derived based on the number of years and the number of months collected in eCRF, age categories (<=27 days, 28 days - <=23 months, 2-11 years, 12-17 years), baseline pregnancy test (if applicable), height, weight and body mass index will be summarized by treatment groups. All subjects will be summarized and listed for type of intervention (i.e., parenchymous surface of liver or soft tissue), intensity of the bleeding at TBS (i.e., Grade 1 = mild or Grade 2 = moderate) and size of the approximate bleeding surface at TBS (small; medium; and large). The date/time of induction of anesthesia, skin incision, and recovery from anesthesia for all surgery types will also be listed.

Page 13 of 18

7.2 Medical and Surgical History

Medical and surgical history will be coded using the Medical Dictionary for Regulatory Activities (MedDRA) and summarized/listed by treatment groups.

8 CONCOMITANT MEDICATION AND TREATMENT

8.1 Prior and Concomitant Medication

All medications including topical hemostats and blood products will be coded using ATC classification codes via the World Health Organization Drug classification Dictionary. All medications will be summarized by treatment groups and sorted alphabetically by medication class (i.e., ATC level 2) and medication sub-class (i.e., ATC level 4). If the ATC level 4 term is missing, the ATC level 3 term will be used in the medication summary table and data listing.

The following convention will be used for missing or partial end date information in order to determine whether a medication is prior or concomitant:

The unknown portions of a medication end date will be assumed to be as late as possible. If a medication end date is incomplete but the month/year of medication end date is prior to the month/year of the start of study treatment, then the medication will be considered a prior medication. If a medication end date is incomplete but the month/year of medication end date is the same as the month/year of the start of study treatment, then the medication will be considered a concomitant medication. All other incomplete medication end dates and all medications with missing end dates will be assumed to be concomitant medications. The unknown portions of a medication end time will be assumed to be as late as possible. Start/end dates and time reported in the eCRFs will be presented in the listings.

Prior medications are defined as any medication ended prior to the start of study treatment (i.e., application of FS Grifols or EVICEL).

Concomitant medications are defined as any medication started on or after the start of study treatment, or any medication taken prior to the start of study treatment and continued after the start of study treatment during the study.

All medications including topical hemostats and blood products will be listed.

8.2 Extent of Study Treatment Exposure

The extent of study treatment exposure in mL to TBS will be summarized for FS Grifols and EVICEL treatment groups.

The estimated total quantity in mL (i.e., Kit #1 volume in mL x estimated percentage volume applied to TBS + Kit #2 volume in mL x estimated percentage volume applied to TBS) of FS Grifols and EVICEL will be summarized.

Page 14 of 18

The volume of each kit and estimated percentage volume applied to TBS will be listed.

The mode of application (i.e., drip or spray) will be listed and summarized.

9 EFFICACY ANALYSIS

The efficacy analyses will be performed using the mITT population. Additionally, the primary efficacy endpoint of the proportion of subjects achieving hemostasis by 4 minutes at TBS will be analyzed using the PP population (if different from mITT population). As sensitivity analysis, the primary efficacy endpoint will be analyzed using ITT population. For subjects in both treatments in the ITT population who do not meet the intra-operative criteria and do not receive the study treatment, they will be deemed not achieving hemostasis for the primary efficacy endpoint.

9.1 Primary Efficacy Analysis

The primary efficacy variable is the proportion of subjects achieving hemostasis by T₄ based on its nominal scheduled time point at TBS.

Assuming that T is the response rate for the FS Grifols treatment group, C is the response rate for the EVICEL group (control group), M is the pre-specified non-inferiority margin.

The null hypothesis (H_0) is: Risk Ratio $(T/C) \le 1$ -M and

the alternative hypothesis (H₁) is: Risk Ratio (T/C) \geq 1-M,

where 1-M is 0.8.

The primary efficacy endpoint will be analyzed using Cochran-Mantel-Haenszel (CMH) test stratified by type of surgery (i.e., parenchymous surface of liver versus soft tissue surgery). The ratio of proportion (RR_{pooled}) of subjects meeting the primary efficacy endpoint in the two treatment groups (FS Grifols relative to EVICEL) and its two-sided asymptotic 95% confidence interval (CI) will be provided:

$$RR_{pooled} = \frac{\sum_{i} a_{i} * m_{0i} / N_{i}}{\sum_{i} b_{i} * m_{1i} / N_{i}}$$

The asymptotic 95% confidence interval of RR_{pooled} is calculated as:

Lower limit =
$$\exp\{\ln(RR_{pooled}) - Z_{\alpha/2} * SE\}$$

Upper limit =
$$\exp\{\ln(RR_{pooled}) + Z_{\alpha/2} * SE\}$$

Where the standard error (SE) is calculated as:

Grifols Worldwide Operations, Ltd Page 15 of 18
$$SE = \sqrt{\frac{\sum_{i} (n_{1i} * m_{1i} * m_{0i} - a_{i} * b_{i} * N_{i}) / N_{i}^{2}}{(\sum_{i} a_{i} * m_{0i} / N_{i})(\sum_{i} b_{i} * m_{1i} / N_{i})}}$$

where a_i , b_i , c_i , d_i , n_{1i} , n_{0i} , m_{1i} , m_{0i} , and N_i are the number of subjects defined in following table; i = 1 or 2 according to different types of surgeries (i.e., parenchymous surface of liver or soft tissue surgery).

		FS Grifols	EVICEL	Total
Hemostasis	Yes	$a_{\rm i}$	b_{i}	n_{1i}
achieved?	No	c_{i}	d_i	n_{0i}
Total		m_{1i}	m _{0i}	Ni

The non-inferiority will be deemed to have been demonstrated if the lower limit of the 95% CI exceeds 0.8. After the non-inferiority of FS Grifols to EVICEL is established, its superiority may be additionally claimed if the 95% CI for the ratio is entirely above 1.

In this study, 2 types of applicator devices are used to apply FS Grifols (Fibrijet® device up to 30 November 2019, VistaSealTM Dual Applicator thereafter). A sensitivity analysis for the primary efficacy endpoint using mITT will be performed for the subgroups based on the use of different applicators, to compare FS Grifols-treated subjects with either type of applicator device vs the Evicel treatment group. A subgroup analysis by surgery type will also be provided for this by applicator type analysis.

If any missing hemostatic assessment at TBS at T₄ for a randomized subject occurs, it will be treated as non-hemostasis at TBS at T₄ for the subject in the primary efficacy analysis. A sensitivity analysis with non-missing observational hemostatic assessment at TBS at T₄ will be performed.

Considering that the hemostasis assessment may not be performed exactly at the scheduled time point, as supportive analyses, the primary efficacy variable based on the time window below will also be analyzed using the CMH test. The hemostasis assessment data at each time point will be classified into the appropriate category based on the time window in the table below, according to the elapsed time of hemostasis assessment from the start of initial treatment application (T_{Start}) to T₄, T₇ and T₁₀ time points in eCRF.

Scheduled Event	Time Window (MM:SS)
T ₄ (4 minutes from start of application)	<=4:10
T ₇ (7 minutes from start of application)	>=4:11 to <=7:10
T_{10} (10 minutes from start of application)	>=7:11 to <=10:10

Grifols Worldwide Operations, Ltd

Page 16 of 18

If multiple hemostasis assessments fall within the same time window, for purpose of the supportive analyses, the following two scenarios will be considered:

- (a) the first hemostasis assessment will be selected;
- (b) the last hemostasis assessment will be selected.

If there is no hemostasis assessment within a specific time window, the last hemostasis assessment within the previous time window will be carried forward. If there is no hemostasis assessment within the first time window (\leq =4:10), the hemostasis assessment will be deemed non-hemostasis success at T₄. The hemostasis assessment with the elapsed time from T_{Start} greater than 10 minutes and 10 seconds will be classified into the period that is after the 10-minute observational period and before the T_{Closure}.

For primary efficacy endpoint, subgroup analyses will be provided for surgery type, age group, gender, race, baseline TBS bleeding intensity, and TBS size category.

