# Primary Efficacy Analyses

The efficacy analyses will be performed using the mITT population. Additionally, the primary efficacy endpoint will be also analyzed using the PP population (if different from the mITT population). For sensitivity analysis, the primary efficacy endpoint will be analyzed using ITT population. For subjects in both treatment groups in the ITT population who do not meet the intra-operative criteria and do not receive the study treatment, they will be deemed as not achieving hemostasis for the primary efficacy endpoint.

The primary efficacy endpoint of hemostasis at TBS by T4 will be analyzed using the Cochran-Mantel-Haenszel (CMH) test stratified by type of surgery (i.e., parenchymous versus soft tissue surgery). The ratio of the proportion of subjects meeting the primary efficacy endpoint in the 2 treatment groups (FS Grifols relative to EVICEL) and its 2-sided asymptotic 95% confidence interval (CI) will be provided. The non-inferiority will be deemed to have been demonstrated if the lower limit of the 95% CI exceeds 0.8. After the non-inferiority of FS Grifols to EVICEL is established, its superiority may be additionally claimed if the 95% CI for the ratio is entirely above 1.

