# 4.3.2 Randomization

Subjects satisfying all pre-operative enrollment criteria will be randomized in 1:1 ratio into the FS Grifols or EVICEL treatment groups. Randomization will be stratified by type of surgery (i.e., parenchymous versus soft tissue surgery) and age groups (i.e., 12-17 years, 2-11 years, 28 days-23 months, and 0-27 days). The investigator site pharmacy will use an Interactive Response Technology (IRT) system to obtain the randomization number and the corresponding assigned treatment (FS Grifols or EVICEL).

At the beginning of the surgical procedure, before any TBS is identified, all materials needed for FS Grifols or EVICEL application will be ready for use. If the subject meets the intra-operative eligibility criteria defined in Section 5.1 and Section 5.2, a randomization number will be recorded in the subject's source documents and electronic Case Report Form (eCRF). If the subject does not meet the intra-operative eligibility criteria, the study drug prepared by the pharmacist will remain unused and discarded according to the respective site standard

procedures. In this case, the IRT system will automatically assign the same treatment to the next subject enrolled in the same stratum.

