# 9.1.2 Efficacy Analysis

The primary efficacy analyses will be performed using the Modified Intent-to-Treat (mITT) population (see Section 9.5 for the definition of the mITT population). Additionally, the primary efficacy endpoint will be also analyzed using the Per-Protocol (PP) population (if different from the mITT population, see Section 9.5 for the definition of the PP population). For sensitivity analysis, the primary efficacy endpoint will be analyzed using the Intent-to-Treat (ITT) population (see Section 9.5 for the definition of the ITT population). For subjects

in both treatment groups in the ITT population who do not meet the intra-operative criteria and do not receive the study treatment, they will be deemed as not achieving hemostasis for the primary efficacy endpoint.

The primary efficacy endpoint of hemostasis at TBS by T4 will be analyzed using the Cochran-Mantel-Haenszel (CMH) test stratified by type of surgery (i.e., parenchymous versus soft tissue surgery). The ratio of the proportion of subjects meeting the primary efficacy endpoint in the 2 treatment groups (FS Grifols relative to EVICEL) and its 2-sided asymptotic 95% CI will be provided. The non-inferiority will be deemed to have been demonstrated if the lower limit of the 95% CI exceeds 0.8. After the non-inferiority of FS Grifols to EVICEL is established, its superiority may be additionally claimed if the 95% CI for the ratio is entirely above 1.

Secondary efficacy endpoints will be analyzed by similar methods at other individual assessment time points (i.e.,  $T_7$  and  $T_{10}$ ).

Exploratory efficacy endpoints will be descriptively summarized by treatment group. The proportion of subjects achieving at least 1 point decrease in bleeding intensity according to the 5-point validated bleeding severity scale by each of the defined observation time points (i.e., T4, T7 and T10) will be analyzed using CMH test stratified by type of surgery (i.e., hepatic versus soft tissue surgery).

Also, an ordered categorical analysis of the hemostatic status at each of the assessment time points (i.e.,  $T_4$ ,  $T_7$  and  $T_{10}$ ) will be presented. For this, the subjects will be assigned to 1 of 4 categories on the basis of their TTH (0 to  $\leq$ 4 minutes;  $\geq$ 4 to  $\leq$ 7 minutes;  $\geq$ 7 to  $\leq$ 10 minutes;  $\geq$ 10 minutes).

Prevalence of treatment failures will be summarized and analyzed by treatment group.

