9.2 Secondary Efficacy Analyses

Analyses relating to secondary efficacy variables, the cumulative proportions of subjects achieving hemostasis by other individual assessment times (i.e., 7 minutes and 10 minutes), will be similarly analyzed using CMH test.

The proportion of subjects with treatment failures will be summarized and analyzed using CMH test.

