9.3 Exploratory Efficacy Analyses

Exploratory efficacy endpoints will be descriptively summarized by treatment group. The proportion of subjects achieving at least 1 point decrease in bleeding intensity according to the 5-point validated bleeding severity scale by each of the defined observation time points (i.e., T4, T7 and T10) will be analyzed using CMH test stratified by type of surgery (i.e., hepatic versus soft tissue surgery).

Also, an ordered categorical analysis of the hemostatic status at each of the assessment time points (i.e., T4, T7 and T10) will be presented. For this, the subjects will be assigned to 1 of 4 categories on the basis of their time to hemostasis (0 to \leq 4 minutes; \geq 4 to \leq 7 minutes; \geq 7 to \leq 10 minutes; \geq 10 minutes). The comparison between treatment groups will be done using an ordinal logistic model assuming proportional odds.

Change from baseline in bleeding intensity according to the 5-point validated bleeding severity scale at the defined observation time points (i.e., T4, T7 and T10) will be summarized. The 5 grades (i.e., 0, 1, 2, 3, and 4) will be considered continuous values in this analysis.

Page 17 of 18

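### Age group is a randomization stratum but is left out of the primary stratified ratio and interval without a reason, which gives up precision if age affects hemostasis

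*SAP*

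**What the plan says.** Protocol 4.3.2: "Randomization will be stratified by type of surgery (i.e., parenchymous versus soft tissue surgery) and age groups". The age groups are 12-17 years, 2-11 years, 28 days-23 months and 0-27 days, so there are 2 x 4 = 8 randomization strata.

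SAP 9.1: the primary endpoint "will be analyzed using Cochran-Mantel-Haenszel (CMH) test stratified by type of surgery". The formulas for the pooled ratio and its standard error sum over two strata, both defined by surgery type. Protocol 9.1.2 and the synopsis (Primary Efficacy Analyses) give the same single factor.

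Age appears in the primary endpoint analysis only at the end of SAP 9.1, where "subgroup analyses will be provided for surgery type, age group, gender, race, baseline TBS bleeding intensity, and TBS size category". The other analyses of this endpoint in SAP 9 and 9.1 (per-protocol, ITT, applicator type, observed cases, time windows) do not add age as a stratum. Neither document explains the omission.

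For the other endpoints, SAP 9.3 names surgery type as the only stratum for one exploratory test. SAP 9.2 names none: T7 and T10 are to be analyzed in a similar way, and "The proportion of subjects with treatment failures will be summarized and analyzed using CMH test".

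**The concern.** Randomizing within age groups balances age between the arms, so age differences in success contribute little to the chance variation of the estimated ratio. A standard error computed over surgery type alone does not know this. It treats the spread of success rates across ages as random error, so the interval is wider than the true variability of the estimate warrants.

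The trial runs from preterm newborns to 17-year-olds, and the sponsor thought age important enough to balance on. The lower limit of this interval decides non-inferiority, so unneeded width costs power. The choice also has to be made before unblinding, because an age-adjusted interval added afterwards would be post hoc.

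**Working it through.** **Inputs from the documents.** 86 + 86 subjects, 80% success in both arms, and non-inferiority if the lower 95% limit of the ratio exceeds 0.8 (SAP 4.3 and 9.1). Age mix 100/50/16/6 (SAP 4.3, starting with "Adolescents (12 to 17 years): approximately 100"). Protocol 9.2 instead gives ranges: 50-100, 50-100, 16-100 and up to 10. About 50% hepatic surgery (Protocol 4.2).

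**Step 1: the plan's own power.** For an unstratified log ratio:

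- SE = sqrt(2(1 - p)/(p n)) = sqrt(2 x 0.2/(0.8 x 86)) = 0.0762
- Power = Phi(-ln 0.8/SE - 1.96) = Phi(0.2231/0.0762 - 1.96) = 83.3%

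The stated power of at least 80% is reproduced and does not depend on age.

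**Step 2: assumed age effects.** The documents give no T4 success rates by age. Let f be the fall from adolescents to infants, with children one third of the way down and newborns equal to infants. Holding the overall rate at 80% gives an adolescent rate of 0.80 + f x (50/3 + 22)/172. For f = 30 points the rates are 86.7/76.7/56.7/56.7%. For f = 50 they are 91.2/74.6/41.2/41.2%.

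**Step 3: simulation.** 40,000 trials per scenario with the SAP's formulas for RR_pooled and SE. Each trial had 172 subjects, surgery type random at 50%, blocks of 4 within the eight randomization strata (block size is not given, so assumed) and no surgery effect. The analyses compared used two strata (as planned) and six (surgery type x age, with newborns pooled with infants).

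SAP age mix, true ratio 1:

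| Fall in success | Power, 2 strata | Power, 6 strata | Gain (points) |
|---|---|---|---|
| 0 | 82.4% | 82.4% | 0.0 |
| 10 | 82.5% | 82.7% | 0.2 |
| 20 | 82.9% | 83.6% | 0.7 |
| 30 | 83.0% | 84.7% | 1.7 |
| 40 | 83.9% | 86.7% | 2.8 |
| 50 | 84.8% | 89.2% | 4.4 |

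A younger mix inside the protocol's ranges (60/60/46/6) gives gains of 0.3, 1.0, 2.4 and 4.0 points for falls of 10, 20, 30 and 40.

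**Step 4: where the gain comes from.** With a 50-point fall, the planned SE averages 0.0764 while the true SD of the log ratio is 0.0704. The SE is therefore 0.0764/0.0704 - 1 = 8.5% too large. The six-stratum SE (about 0.0695) is close to its own SD (about 0.0696 to 0.0704 across runs). With no age effect, the mean SE moves from 0.0764 to 0.0765.

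**Step 5: error at the margin.** At a true ratio of 0.8 (nominal 2.5%), rejection with the SAP mix is 2.3-2.8% with two strata and 2.7-3.0% with six. With no age effect, both are 2.7%. Repeat runs with other seeds put the six-stratum figure for a 50-point fall between 3.0% and 3.3%.

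**Step 6: number of strata.** Six and eight strata differ by at most 0.2 power points. With eight, about 34% of simulated trials had a stratum with one arm empty. Such a stratum adds zero to both sums in RR_pooled, so its subjects drop out of the estimate.

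**The case against.** The strongest reply is that nothing is broken. The planned interval is valid and slightly conservative, which is defensible in a non-inferiority trial, and the stated power is met. That is right, and this point claims no more than lost precision.

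Second, the estimate itself hardly changes. Its SD with two against six strata is 0.0748 against 0.0745 for a 30-point fall, and 0.0706 against 0.0698 for 50. Mainly the reported SE shrinks, so part of the power gain is a move from a conservative test to one slightly above nominal. If both methods are calibrated to 2.5%, the gains fall to about 0.2, 0.6, 1.1 and 1.7 points for falls of 20, 30, 40 and 50. This stands, and it means over half of each raw gain is recovered conservatism. It does not defeat the change: about 3% at the margin is close to the 2.7-2.9% that the planned interval already gives when age has no effect.

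Third, the age effects are assumed, while the documents do support surgery type as a stratum: FS Grifols success by T4 was 92.8% in parenchymous and 82.8% in soft tissue surgery (Protocol 2.2.1.2 and 2.2.1.3). This also stands. For falls of 10 to 20 points the gain is below one point with the SAP mix.

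Fourth, about 6 newborns split over two surgery types make sparse cells, which could justify collapsing age. That supports pooling the two youngest groups. It does not require dropping age entirely, and the documents do not offer it as a reason.

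Finally, the age subgroup analyses do not alter the primary interval. The wording for T7 and T10 in SAP 9.2 can reasonably be read as carrying over the strata of 9.1, but the treatment-failure analysis names no strata.

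**Conclusion.** The point holds: the primary analysis omits a randomization factor without explanation, and if age is prognostic its interval is wider than it need be. This concerns precision and pre-specification. It is not a validity defect, and the sample size stands.

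The size is unknown because the documents give no success rates by age. Under the assumptions above, the raw power gain is nil with no age effect, under one point for falls up to 20 points, about 1.7 points for 30 and about 4.4 for 50 with the SAP mix. It is somewhat larger for a younger mix. The figures rest on an overall rate of 80%, blocks of 4 and no surgery effect. The change is worth making because it costs almost nothing, but on its own it does not compel a protocol amendment.

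**What to change.** **Preferred.** In SAP 9.1, Protocol 9.1.2 and the synopsis, stratify the primary ratio and interval by surgery type and age group. Fix before unblinding that 0-27 days is pooled with 28 days-23 months, so the index runs over six strata. A fixed rule is better than one that depends on realised enrolment. Keep the surgery-type-only analysis as supportive, and name the same strata in SAP 9.2 (T7, T10, treatment failures) and 9.3.

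**SAP-only alternative.** Keep the primary analysis as it is, add the six-stratum version to SAP 9.1 as a pre-specified sensitivity analysis, and state in a sentence why age is left out of the primary one.

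**Cost.** The preferred route changes protocol text and so needs an amendment (Protocol 12.2); the alternative needs only the SAP. Neither needs new data: age group is used by the IRT system and recorded at screening (Protocol 4.3.2 and 7.2.1.1). The statistical price of the preferred route is a mean SE of 0.0765 instead of 0.0764 if age does not matter. If age matters strongly, rejection at the margin moves from about 2.3% to about 3.0%.
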